Cardiometabolic Effects of Pecans as a Snack

NCT05071807

September 19, 2023

The sample size calculation was based on FMD, the primary outcome. To detect a 1.2 percentage point (standard deviation 2.4; effect size 0.5) between-group difference in the change in FMD with 80% power ($\alpha=0.05$), it was estimated that a sample size of 128 participants was needed (64 per group) (40-43).

All analyses were performed in SAS (version 9.4; SAS Institute Inc.). All data collected from randomly assigned participants were included in data analyses consistent with intent-to-treat principles. All residuals for regression models were checked for normality via normal probability (Q-Q) plots. When the residuals were non-normally distributed, log transformation was conducted, which improved the residual distribution to approximately normal. Linearity was investigated by plotting model residuals against the outcome of interest and for all variables the assumption of linearity was met. All models were adjusted for outcome baseline value, age (years), sex (male or female) and baseline BMI (kg/m²). For all described tests, effect modification by sex was examined by evaluating the group by sex interaction. If the group by sex interaction main effect was not significant it was excluded from the final model. The primary analyses for the vascular and cardiometabolic outcomes assessed between group (pecan or usual diet) differences in the change from baseline. The change from baseline was calculated by subtracting the endpoint value from the baseline value. Weight, lipids/lipoproteins, glucose and insulin were measured on two test days at each time point and values were averaged for analysis to improve measurement precision. Between-group differences in the change from baseline for all vascular and cardiometabolic outcomes were assessed using linear regression models.

For diet quality, linear mixed models were used to account for the repeated nature of the outcome. Group was included as a fixed effect and time point was included as a repeated effect. Intervention effects were determined by examining the group by visit interaction. When a significant group by time point interaction was detected, post hoc testing was conducted and the Tukey-Kramer method was used to adjust for multiple comparisons. Statistical significance was set at $p < 0.05$.

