2.0 Background

2.1 Scientific Background and Gaps

Describe the scientific background and gaps in current knowledge.

For clinical research studies being conducted at Penn State Health/Penn State College of Medicine, and for other non-PSH locations as applicable, describe the treatment/procedure that is considered standard

of care (i.e., indicate how patients would be treated in non-investigational setting); and if applicable, indicate if the study procedure is available to patient without taking part in the study.

Current Dietary Guidelines for general health and prevention of chronic disease recommend a healthy dietary pattern U.S. Department of Health and Human Services (2016). In the U.S., habitual dietary patterns do not align with recommended health dietary patterns. Further, diet quality is suboptimal and thus strategies are needed to improve overall diet quality. The proposed trial aims to examine the cardiometabolic effects of pecans, when replacing a habitual snack. This trial will test the hypothesis that dietary incorporation of pecans to replace typical U.S. snack foods will improve diet quality and confer cardiometabolic benefits.

Pecans have the highest polyphenol content of any nut containing 1816 mg/100g (Ros, 2015). A significant proportion of the polyphenol content is flavanols (494 mg/100g), which are present in higher quantities than dark chocolate (246 mg/100g), blueberries (332 mg/100g) and red wine (313 mg/100g) (Gu et al., 2004). A meta-analysis of 11 studies showed that flow mediated dilation (FMD), a measure of endothelial function, increased by 1.34% after 2-18 weeks of consuming chocolate/cocoa/flavanols (Hooper et al., 2012). This change in FMD is clinically significant; for every 1% increase in FMD, the risk of CVD is reduced by 12% (Matsuzawa, Kwon, Lennon, Lerman, & Lerman, 2015). Furthermore, Balzer et al. showed flavanol rich cocoa containing 371 mg or 963 mg of flavanols improved FMD for 2 to 3 hours after consumption; consumption of 963 mg of cocoa flavonols for 30 days increased FMD by ~30% (Balzer et al., 2008). In the proposed study, the subjects will consume approximately 212 mg of flavanols (781 mg total polyphenols) from pecans as part of the healthy dietary pattern. Therefore, based on previous studies of phenolic rich foods, we hypothesize that the polyphenols in pecans will act on the vasculature to improve endothelial function.

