8.3 Statistical methods

Describe the statistical methods (or non-statistical methods of analysis) that will be employed.

The normality of the data will be tested before performing analyses, and transformations will be made if needed. In the primary analyses, the change in outcome measures (baseline to 12 weeks) will be compared between groups after adjustment for baseline value, age, sex, and BMI. The mixed model

procedure will be used (SAS) with randomization as a fixed factor, and baseline value for the outcome measure, age, sex, and BMI included as covariates.

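### Does the SAP's log-transformation rule threaten the primary FMD analysis or its percentage-point scale?

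*SAP*

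**What the plan says.** The SAP checks the residuals of its regression models with Q-Q plots and gives one remedy: "When the residuals were non-normally distributed, log transformation was conducted, which improved the residual distribution to approximately normal". The same paragraph places FMD under these models: "Between-group differences in the change from baseline for all vascular and cardiometabolic outcomes were assessed using linear regression models". On who is analysed it says: "All data collected from randomly assigned participants were included in data analyses consistent with intent-to-treat principles". The design target is on the raw scale: "To detect a 1.2 percentage point (standard deviation 2.4; effect size 0.5) between-group difference in the change in FMD with 80% power".

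Protocol section 8.3 is no more specific: "The normality of the data will be tested before performing analyses, and transformations will be made if needed". Protocol section 2.1 reads FMD in absolute units, stating that "for every 1% increase in FMD, the risk of CVD is reduced by 12" per cent.

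Neither document names the logged outcomes or the logged quantity. Neither says that FMD stayed in percentage points.

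**The concern.** The modelled outcome is a signed change, and a log does not exist at or below zero. If the change itself was logged, a large part of the sample would drop out, and the claim that all randomised data were used would fail for that model. If each visit's value was logged first, the contrast becomes a ratio. A ratio has no fixed equivalent to the 1.2-point target, or to the protocol's per-1% reading, until an FMD level is supplied, and the documents give none. On either reading, the scale of the primary effect would depend on how a residual plot looked. That is a fair question to put to a primary analysis.

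**Working it through.** **Design figure.** Inputs from the SAP: difference 1.2, SD 2.4, 80% power, alpha 0.05 (taken as two-sided). Normal approximation: 2 × (1.96 + 0.84)² / 0.5² = 62.7, so 63 per arm. The t-test solution is 63.77, so 64 per arm and 128 in all, with power 0.801. The stated size is reproduced on the raw scale, and the log rule does not affect it.

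**Reading 1: the change is logged.** Assume normal changes with SD 2.4, mean 0 in control and a difference of 1.2.
- Control: P(change ≤ 0) = 0.50.
- Pecan arm, endpoint minus baseline: Φ(−1.2/2.4) = 0.309. Undefined values: 64 × (0.50 + 0.309) ≈ 52.
- Pecan arm, baseline minus endpoint (as the SAP words it): 0.691. Undefined values: 64 × (0.50 + 0.691) ≈ 76.

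Losing 52 or 76 of 128 values does not fit an analysis reported as using all randomised data, nor a log reported as making residuals approximately normal. This reading can be set aside.

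**Reading 2: each visit's value is logged.** Strictly positive markers lose nobody. For FMD the level and spread are not in the documents, so means of 4, 6 and 8 and visit SDs of 2.4 to 3.0 are assumed. The table gives expected participants of 128 with any FMD at or below zero.

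| Mean FMD | Normal FMD | Normal baseline, chi-square(2) residuals |
|---|---|---|
| 4 | 9-16 | 6-12 |
| 6 | 1-4 | 1-3 |
| 8 | 0-1 | 0-0.5 |

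The first column describes data that would seldom call for a log: with normal FMD, a Shapiro-Wilk test (a stand-in for the SAP's visual check) flags only 5% of runs, its nominal rate. The second column is flagged in 100% of runs. With log-normal FMD, flagged in 83-100%, the loss is zero by construction.

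**Scale.** Ratio for +1.2 points = (b + 1.2)/b: 5.2/4 = 1.30, 7.2/6 = 1.20, 9.2/8 = 1.15. Conversely, a ratio of 1.20 is 0.2 × b = 0.8, 1.2 or 1.6 points. The conversion needs b, which the trial measures at baseline (protocol 7.1 and 7.2.3), so an approximate reading in points will be available with the results.

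**Type I error.** ANCOVA of change on group and baseline, 64 per arm, residual SD 2.4, 8,000 runs, untransformed: 0.045 for t(3), 0.056 for chi-square(2) and 0.046 for lognormal residuals. With both scales side by side under skewed or heavy-tailed residuals: 0.045-0.054 in points and 0.045-0.058 for the per-visit log.

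**Power at 1.2 points.**
- Untransformed, residual SD 2.4: 0.836, 0.805 and 0.813 for the same three residual shapes.
- Visit SD 2.4 and baseline-to-follow-up correlation 0.5: residual SD = 2.4 × √(1 − 0.25) = 2.08, so power is higher on both scales. Chi-square(2): log 0.96-0.99 against about 0.89 in points. t(3): log 0.88-0.89 against 0.90-0.91.
- Normal FMD, simple test on change: log 0.58-0.63 against about 0.80. This is the setting where the rule is rarely triggered.

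**The case for a change.** The strongest case is that a primary outcome should have its scale fixed in advance. The untransformed model is valid at 64 per arm even with clearly non-normal residuals, so the log protects nothing that needs protecting. Keeping FMD in points, with robust standard errors as a sensitivity analysis, would take a few sentences and remove all doubt. Because the SAP is in the past tense and lists no logged outcomes, its reader cannot tell what was done.

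Part of this stands. The detail is missing, and one sentence would have supplied it. The untransformed test is sound, and a fixed point scale would be a respectable choice.

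The rest does not make the plan wrong. The log also holds its error rate, and under right skew it has the greater power, so insisting on points is a trade-off. The trigger is residual shape, not the treatment contrast, though the simulations tested each scale separately and not the two-step choice. Robust errors, a bootstrap and modelling log week-12 values are good options, but leaving them out produces no demonstrated error.

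**Conclusion.** No change to the plan is needed. The SAP leaves unstated which outcomes were logged and on what quantity, and analysts would fill that gap sensibly: a log of positive, skewed markers at each visit, with logged outcomes identified when results are reported. Nothing in the documents shows that FMD was logged, that any participant was lost, or that an error rate was disturbed.

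If FMD was logged, simulated type I error stays between 0.045 and 0.058. The main cost is reading a ratio of about 1.15 to 1.30 against a 1.2-point target, with baseline FMD in hand.

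This rests on assumed FMD means of 4 to 8 and visit SDs of 2.4 to 3.0, on the residual shapes simulated, and on taking the SAP at its word that all randomised data were included. At a mean near 4, a per-visit log could still lose 6 to 12 participants under skew. A reader can check by seeing whether FMD is reported in percentage points and how many participants its model includes. The diet-quality analysis and the sample size are not affected.

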7.1 Study Design

Describe and explain the study design.

A two-arm randomized parallel study is proposed. Subjects will be randomized to one of the following attention and resource matched conditions for approximately 12-weeks: 1) education to consume 2 oz./day of pecans in place of the snacks they usually eat (AAD+P); 2) continue consuming their current diet (AAD) with provision gift cards worth \$30 monthly (equivalent value to the pecans) and matched contact with study personnel.

Assessment of outcomes will occur at baseline and the end of the treatment period (week 12). Pre-menopausal women will be scheduled for testing within 7 days of starting their menstrual period to control for hormonal effects on vascular function. Therefore, the treatment periods may be adjusted as needed. At the baseline and 12-weeks two blood samples will be collected (separated by at least 24-hours) for endpoint analysis. Weight will be measured on both days at each timepoint. Flow mediated dilation, central and peripheral blood pressure and pulse wave velocity will be measured on one day at each time point. Diet intake will be assessed at baseline, week 6, and week 12 using 24-hour recalls. Subjects will also provide a fecal collection at baseline and 12 weeks.

7.2

Study Procedures

Provide a step by step description of all research procedures being conducted (broken down by visit, if applicable) including such information as below (where and when applicable); describe the following:

- HOW: (e.g., data collection via interviews, focus groups, forms such as surveys and questionnaires, medical/school records, audio/video/digital recordings, photographs, EKG procedures, MRI, mobile devices such as electronic tablets/cell phones, observations, collection of specimens, experimental drug/device testing, manipulation of behavior/use of deception, computer games, etc.)
- WHERE: (e.g., classrooms, labs, internet/online, places of business, medical settings, public spaces, etc.)

[Type protocol text here]

7.2.1 Visit 1 or Day 1 or Pre-test, etc.

Provide a description of what procedures will be performed on visit 1 or day 1 or pre-test in order of how these will be done. If your study only involves one session or visit, use this section only and indicate 7.2.2 as not applicable.

Participants will be consented prior to any screening activities.

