Screening: This visit will occur at the Clinical Research Center, Noll Laboratory. The clinical visit will consist of filling out forms (medical history, personal information); measuring waist circumference and height and weight so that BMI can be calculated and blood pressure will be measured to determine eligibility. Women of child-bearing potential will provide a urine sample for a pregnancy test. A blood sample will be taken and a complete blood count, and a blood lipid panel will be performed (approximately 19 ml of blood or ~1.25 tablespoon will be taken). If the initial blood draw is unsuccessful it may need to be repeated, with permission from the participant. In addition, if a potential participant takes thyroid medicine they must provide a current (within 6 months) lab test. If they do not have one, an extra 3.5 ml (0.2 Tbsp) of blood will be taken to conduct a thyroid test. If all eligibility criteria are met, participants will be scheduled for their baseline measurements. Baseline visits typically occur within 1-2 weeks following the screening appointment. Participants will be provided with one of two standardized meals with foods commonly consumed in the American diet prepared in the metabolic diet center kitchen to consume the evening before their Day 2 visit. The meal options will be Mediterranean chicken with potatoes and broccoli OR a black bean quesadilla with broccoli.

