8.0 Number of Subjects and Statistical Plan

8.1 Number of Subjects

Indicate the maximum number of subjects to be accrued/enrolled. Distinguish between the number of subjects who are expected to be enrolled and screened, and the number of subjects needed to complete the research procedures if applicable (i.e., numbers of subjects excluding screen failures.)

A sample size of 128 (64 per group) is needed. To complete 128 individuals, approximately 140 participants will be recruited to account for an anticipated ~10% dropout rate.

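### The peripheral blood pressure and standard lipid models use only one pre-treatment value of the outcome, although a screening value is already collected; adding it could sharpen these secondary comparisons at almost no cost.

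*SAP*

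**What the plan says.** The SAP's analysis paragraph fixes one covariate set: "All models were adjusted for outcome baseline value, age (years), sex (male or female) and baseline BMI". Protocol 8.3 lists the same four. Neither mentions a screening measurement.

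Protocol 7.2.1 describes the screening visit. There, "blood pressure will be measured to determine eligibility", and "A blood sample will be taken and a complete blood count, and a blood lipid panel will be performed". People who meet all criteria are then booked for baseline, typically one to two weeks later. The documents do not state the moment of randomisation, but screening comes before baseline and before treatment.

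For the outcome visits, Protocol 7.1 says that "central and peripheral blood pressure and pulse wave velocity will be measured on one day at each time point"; section 7.2.2 adds that the blood pressure test is done in triplicate on that day. Lipids are drawn on two test days at each time point, and the SAP averages the two values for precision. Protocol 1.3 names peripheral and central blood pressure and the four standard lipids as secondary endpoints.

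**The concern.** A single day's blood pressure carries that day's variation as well as the person's usual level. Triplicate readings reduce the noise within a visit but not the variation between days. A second pre-treatment occasion recovers part of what that noise hides, and the trial already has one.

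The SAP accepts this reasoning for lipids, glucose, insulin and weight, which it averages over two days. Peripheral blood pressure gets no second day, and the screening values of blood pressure and lipids serve eligibility only. At stake is the width of the confidence intervals for six named secondary outcomes: systolic and diastolic pressure, total, LDL and HDL cholesterol, and triglycerides. The trial was sized for FMD alone, so precision on these outcomes was never planned for.

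A value measured before allocation can enter the model without biasing the randomised comparison, even if it was also used to decide eligibility.

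**Working it through.** **The plan's own figure.** The SAP sizes the trial "To detect a 1.2 percentage point (standard deviation 2.4; effect size 0.5) between-group difference in the change in FMD with 80% power", and Protocol 8.1 says "A sample size of 128 (64 per group) is needed". With two-sided alpha 0.05 (sidedness is not stated), the normal approximation gives 2 × (1.960 + 0.842)² × (2.4/1.2)² = 62.8, so 63 per group; the t test gives 63.77, so 64. The figure reproduces. For dropout, the protocol says "approximately 140 participants will be recruited to account for an anticipated ~10% dropout rate"; 128/0.9 gives 143 and 128 × 1.1 gives 141, both close to 140. None of this concerns blood pressure or lipids, for which no power or precision is stated.

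**Set-up.** Baseline is in the model, so analysing change or the week-12 value gives the same residual variance. All correlations below are assumptions, because the documents contain none.

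**Peripheral blood pressure, screening as good a predictor as baseline.** Take one correlation r among screening, baseline and week 12. Residual variance is 1 − r² with baseline alone and 1 − 2r²/(1 + r) with both. The proportional reduction simplifies to [r/(1 + r)]².

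| r | baseline only | with screening | reduction | 128 becomes worth | 80% power becomes |
|---|---|---|---|---|---|
| 0.5 | 0.750 | 0.667 | 11.1% | 144 | 84.4% |
| 0.6 | 0.640 | 0.550 | 14.1% | 149 | 85.6% |
| 0.7 | 0.510 | 0.424 | 17.0% | 154 | 86.7% |

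**Allowing for age, sex and BMI.** These are already in the model and explain part of the stable difference between people. Suppose they explain a share s of the variance at each occasion, all of it common to the occasions. The partial correlation is then (r − s)/(1 − s).
- s = 0.10: partial correlations 0.444, 0.556 and 0.667; reductions 9.5%, 12.8% and 16.0%.
- s = 0.20: partial correlations 0.375, 0.500 and 0.625; reductions 7.4%, 11.1% and 14.8%.

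The favourable range for blood pressure is therefore about 7 to 17%.

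**Peripheral blood pressure, screening the weaker predictor.** Write b for baseline with week 12, c for screening with week 12 and d for screening with baseline. Then R² = (b² + c² − 2bcd)/(1 − d²), against b² for baseline alone.
- b 0.6, c 0.55, d 0.7: R² = (0.36 + 0.3025 − 0.462)/0.51 = 0.393. Residual 0.607 against 0.64, a 5% reduction; about 3 to 4% after the same allowance for age, sex and BMI.
- b 0.6, c 0.5, d 0.6: R² = (0.36 + 0.25 − 0.36)/0.64 = 0.391. Residual 0.609 against 0.64, a 4.8% reduction.
- b 0.7, c 0.5, d 0.7: R² = (0.49 + 0.25 − 0.49)/0.51 = 0.490. Residual 0.510 against 0.510, no gain.

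The gain vanishes when c equals b × d, that is, when screening says nothing about week 12 beyond what baseline already says.

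**Lipids.** Baseline and week 12 are two-day means, and screening is one day. With one day-level correlation r, a two-day mean has variance (1 + r)/2 and a three-day mean (1 + 2r)/3. The residual is (1 + r)/2 − r²/[(1 + r)/2] without screening and (1 + r)/2 − r²/[(1 + 2r)/3] with it.
- r = 0.70: 0.274 to 0.238, a 13.2% reduction.
- r = 0.80: 0.189 to 0.162, a 14.5% reduction.
- r = 0.85: 0.144 to 0.122, a 15.1% reduction.

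These make no allowance for age, sex and BMI, so they are upper values for this correlation structure. Another structure moves them. If the paired days correlate at 0.8 and all other pairs of days at 0.7, the reduction is 14.9%; at 0.9 and 0.8 it is 17.7%. Lower only the screening-to-week-12 correlation, to 0.6 and 0.7 respectively, and these become 1.9% and 0.8%. At 0.75 in the second case the reduction is 6.5%.

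**Cost.** With 128 participants and six coefficients (intercept, group, four covariates), residual degrees of freedom go from 122 to 121. A useless extra covariate costs roughly 1/121, or 0.8%, of variance.

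**The case against.** The strongest reply is that nothing here is an error. The plan already uses baseline-adjusted models with three further covariates, stated alike in both documents, and leaving out a second pre-treatment value creates no bias or contradiction. That is right, and it limits the point to an optional gain in efficiency.

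Four further objections stand in part.
- **The gain is not established.** Screening lies further from week 12 than baseline does, and its values are cut by eligibility limits (systolic above 160 mmHg, diastolic above 100 mmHg and triglycerides of 350 mg/dL or more are excluded). Both may weaken its prediction.
- **Like-for-like measurement is not shown.** Protocol 7.2.2 specifies rest, arm, automated cuff and triplicate readings. The screening text gives no method for blood pressure and does not itemise the lipid panel. Fasting is implied by the glucose criteria but not stated for the lipids.
- **Lipids are largely handled.** The two-day averages already remove much of the day-to-day noise.
- **It may be late.** The SAP, dated September 2023, is written in the past tense.

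A reader might infer that the models adjust for baseline alone, or that the planned intervals are known to be too wide. The SAP lists four covariates, and no correlation in the documents supports a firm statement about width. A reader might also extend the point to central pressure or particle measures. No screening counterpart is described for either, and the value of brachial pressure as a stand-in for central pressure was not calculated.

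**Conclusion.** The point holds as an optional improvement for six secondary outcomes. An already collected, pre-treatment value of the same measure is left out of the peripheral blood pressure and standard lipid models, and including it would not bias the comparison.

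The size is uncertain: near zero to about 7% of residual variance if screening is the weaker predictor; about 7 to 17% for peripheral blood pressure (correlations of 0.5 to 0.7, the low end allowing for age, sex and BMI) and at most about 13 to 15% for lipids (one day-level correlation of 0.7 to 0.85) if screening is interchangeable with baseline. The case is clearest for peripheral blood pressure.

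It would be wrong to read this as bias, or as a weakness in the primary analysis. FMD, PWV and the sample size of 128 are unaffected.

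**What to change.** Add the screening value of the same measure as a fifth covariate in the models for peripheral systolic and diastolic pressure, total, LDL and HDL cholesterol, and triglycerides. Where an outcome is log-transformed, enter its screening value on the same scale. Report the four-covariate model alongside. Leave the FMD, PWV, central pressure and particle models as they are.

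If these outcomes have already been analysed, keep the four-covariate model as the main result and present the extended one as a labelled post hoc sensitivity analysis.

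Confirm first how screening blood pressure was taken and that the screening panel contains all four lipids. The cost is one clause in the SAP and one degree of freedom per model, with no new data collection.

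### In the diet-quality mixed model the intervention term (group-by-visit) and the sex-modification term (group-by-sex) do not match, so one of them is the wrong test whichever role baseline plays

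*SAP*

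**What the plan says.** The SAP's analysis paragraph sets a single rule for sex: "For all described tests, effect modification by sex was examined by evaluating the group by sex interaction". It adds: "If the group by sex interaction main effect was not significant it was excluded from the final model".

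Two kinds of model fall under that rule.

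- Vascular and cardiometabolic outcomes: "Between-group differences in the change from baseline for all vascular and cardiometabolic outcomes were assessed using linear regression models". There is one response per person, the change.
- Diet quality: a linear mixed model, in which "Group was included as a fixed effect and time point was included as a repeated effect" and "Intervention effects were determined by examining the group by visit interaction". Between-arm post hoc comparisons follow only if that interaction is significant.

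Protocol 7.1 gives three assessment times: "Diet intake will be assessed at baseline, week 6, and week 12 using 24-hour recalls". Protocol 1.3 lists diet quality as a secondary endpoint.

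The SAP also says: "All models were adjusted for outcome baseline value, age (years), sex (male or female) and baseline BMI (kg/m²"). It does not say whether, for diet quality, the baseline visit is also one of the repeated responses. No group-by-visit-by-sex term is named.

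**The concern.** In a change-score regression the intervention effect is the group term, so its modification by sex is group-by-sex. That part of the SAP is coherent.

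In the diet-quality model the SAP places the intervention effect in group-by-visit. Modification of that effect by sex is then group-by-visit-by-sex, or an equivalent contrast of changes. The two-way group-by-sex term asks something else: whether the arm difference, averaged over the modelled visits, differs between men and women.

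Two conclusions are at stake. One is whether sex terms are carried into the final diet-quality model, since a non-significant term is dropped. The other, under the alternative reading of baseline, is whether the main diet-quality test detects an intervention effect at all.

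**Working it through.** **The plan's own figure.** For FMD (difference 1.2, SD 2.4, two-sided alpha 0.05, 80% power), the normal approximation gives 63 per group. The t-test gives power 0.795 at 63 and 0.801 at 64. The stated 64 per group reproduces. It enters below only as N = 128.

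**Assumptions not in the documents.** Compound symmetry with between-visit correlation r = 0.3, 0.5 or 0.7; unit SD at each visit; complete data. The absolute power figures also assume a 50:50 sex split and a sex difference in the intervention effect of 0.8 SD.

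**Reading A: baseline is a repeated response and not a covariate.** Group-by-sex works on each person's three-visit mean.

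*Modification of size 1 at weeks 6 and 12.*
- Two-way term: signal (0 + 1 + 1)/3 = 2/3; variance (1 + 2r)/3.
- Matched contrast, mean of weeks 6 and 12 minus baseline: signal 1; variance (1 + r)/2 + 1 − 2r = 1.5(1 − r).
- Relative efficiency = (4/9) × 3/(1 + 2r) × 1.5(1 − r) = 2(1 − r)/(1 + 2r).
- This equals 1 at r = 0.25, so below that value the two-way term loses nothing.

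*Modification at week 12 only.*
- Two-way term: signal 1/3, same variance.
- Matched contrast, week 12 minus baseline: variance 2(1 − r).
- Relative efficiency = 2(1 − r)/[3(1 + 2r)].

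Power of the two-way term where the matched contrast has 80% is Φ(2.80 × √efficiency − 1.96):

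| r | Efficiency, sustained | Power | Efficiency, week 12 only | Power |
|---|---|---|---|---|
| 0.3 | 0.875 | 75% | 0.292 | 33% |
| 0.5 | 0.500 | 51% | 0.167 | 21% |
| 0.7 | 0.250 | 29% | 0.083 | 12% |

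*Absolute power at N = 128.* With 32 people per arm-by-sex cell, the interaction variance is 4/32 = 1/8 of the per-person variance. For the 2-df three-way test, the noncentrality is 8δ′V⁻¹δ, where δ holds the sex differences at weeks 6 and 12 and V is the covariance of the two changes.

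| Sex difference of 0.8 SD | r = 0.3 | r = 0.5 | r = 0.7 |
|---|---|---|---|
| Sustained: group-by-sex (estimates 0.53 SD) | 54% | 46% | 39% |
| Sustained: matched 1-df contrast | 60% | 74% | 92% |
| Sustained: three-way, 2 df | 49% | 64% | 87% |
| Week 12 only: group-by-sex (estimates 0.27 SD) | 18% | 15% | 14% |
| Week 12 only: three-way, 2 df | 49% | 64% | 87% |

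Simulation with 4,000 runs per scenario agreed to within about 3 points. A 70:30 sex split lowers these powers by about 1 to 9 points and leaves the pattern unchanged.

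**Reading B: baseline is a covariate only; weeks 6 and 12 are the responses.** The variance of the two-visit mean given baseline is (1 + r)/2 − r², that is 0.56, 0.50 and 0.36.
- Group-by-sex estimates the full 0.8 SD of a sustained modification. At r = 0.5, 0.8/√(0.50/8) = 3.2 and power is Φ(3.2 − 1.96) = 89%. The other two values are 86% (r = 0.3) and 97% (r = 0.7).
- Group-by-visit now compares the arm difference at week 12 with that at week 6. If the benefit d is the same at both, the contrast is d − d = 0. Power then equals alpha, 5%, and the post hoc comparisons that depend on this test are not reached.

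Under A the sex term is mismatched. Under B the intervention term is.

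**The case against.** The strongest reply is the baseline-adjustment sentence. If the sex rule reaches diet quality because it covers all tests, the adjustment rule reaches it too, and baseline as a covariate with two post-baseline responses is a natural reading. Group-by-sex is then a sound test. That stands, and it rules out saying flatly that the sex term is wrong. It does not clear the plan, because the fault moves to the main diet-quality test. Protocol 8.3 does not settle the matter: it puts baseline in as a covariate, but for the change to week 12, not for a three-visit model.

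A reader might infer that group-by-sex misses real modification altogether. The documents do not support that. Even under reading A the term is diluted, not blind. At r = 0.3 it slightly beats the 2-df three-way test for a sustained difference (54% against 49%), and below r = 0.25 it matches or beats the 1-df contrast. Baseline differences between arms within each sex have expectation zero under randomisation, so they add noise rather than systematic bias.

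A reader might also infer that adding the three-way term is a fix without cost. It is not: under reading B that term tests whether the modification changes between weeks 6 and 12, and it is blind to a sustained one.

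The wording may also be shorthand. The SAP is condensed and uses visit and time point interchangeably, so the fitted model may have held a three-way term. The text cannot confirm this.

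Finally, no aim or hypothesis in Protocol 1.1 concerns sex, Protocol 8.3 names no sex interaction, and the trial is powered only for the FMD main effect. That limits the consequence but not the mismatch.

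**Conclusion.** The point holds for one model and one secondary endpoint. The SAP's two stated diet-quality tests do not form a matching pair, and under either role for baseline one of them is the wrong test.

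- Baseline as a response: the sex term recovers 2/3 of a sustained modification and 1/3 of a week-12-only one. Its power is 75%, 51% and 29% (sustained) or 33%, 21% and 12% (week 12 only), against 80% for the matched contrast.
- Baseline as a covariate: the sex term is right, and the intervention term has no power beyond alpha for an effect equal at weeks 6 and 12.

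The recovered fractions follow from the three visits and equal weighting of them. The power figures rest on compound symmetry and on assumed correlations that the documents do not give. The FMD analysis and the other change-score regressions are not touched. The documents contain no claim that sex effects are absent, so the issue is what such a statement for diet quality could rest on, not an error already reported.

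**What to change.** First, state whether baseline diet quality is a repeated response or a covariate. Then name the pair of tests that belongs to it.

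- **If a response:** keep group-by-visit for the intervention. Test sex by the sex difference in the group contrast of change from baseline, either at week 12 or for the mean of weeks 6 and 12, chosen in advance. Group-by-visit-by-sex with its lower-order terms is an alternative, accepting that this 2-df test can be slightly weaker at low correlation.
- **If a covariate:** keep group-by-sex, and define the intervention effect as the group contrast at weeks 6 and 12 instead of group-by-visit. Do not add the three-way term as the sex test here.

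Restrict the general group-by-sex rule to the change-score regressions.

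The cost is about two SAP sentences and one model rerun, with no new data. If the diet-quality results have already been seen, report the corrected test beside the stated one and say when the choice was made.
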